4 OBJECTIVES AND ENDPOINTS

OBJECTIVES	ENDPOINTS	JUSTIFICATION FOR ENDPOINTS
Primary		
To determine the safety of a multi-faceted ventilator-associated pneumonia diagnostic stewardship bundle.	
Mortality per 1000 mechanically-ventilated patient days
 
Ventilator-associated events (using Centers for Disease Control/National Healthcare Safety Network definitions) per 1000 patient days
 
Median duration of mechanical ventilation per patient.
	The goal of this study is to demonstrate preliminary safety of a diagnostic stewardship bundle for ventilator-associated pneumonia.
Secondary		
To determine the association between a multi-faceted ventilator-associated pneumonia diagnostic stewardship bundle and ICU antibiotic utilization rates.	
Total ICU antibiotic utilization rates (total antibiotic days of therapy per 1000 mechanically-ventilated patient days).
 
Broad-spectrum ICU antibiotic utilization rates (broad-spectrum antibiotic days of therapy per 1000
	Our preliminary data suggests that a bundled diagnostic stewardship intervention can successfully reduce antibiotic use in mechanically-ventilated patients.

OBJECTIVES	ENDPOINTS	JUSTIFICATION FOR ENDPOINTS
	mechanically-ventilated patient days).	
To determine the association between a multi-faceted ventilator-associated pneumonia diagnostic stewardship bundle and rates of positive respiratory cultures.	Positive respiratory cultures per 1000 mechanically-ventilated patient days.	
To assess study feasibility and adherence to protocolized intervention.	Respiratory cultures ordered per 1000 mechanically-ventilated patient days Percentage of respiratory cultures obtained by BAL Percentage of respiratory cultures from BAL samples with alveolar neutrophils <50%	Adherence to study intervention is crucial to evaluating study efficacy and potentially recalibrating approach to intervention prior to multi-center implementation.

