9 STATISTICAL CONSIDERATIONS

9.1 GENERAL STATISTICAL APPROACH

9.1.1 Descriptives

We will compare categorical variables by reporting frequencies and percentages and assess statistical significance using a chi-square test. Subject-level continuous variables will be compared using Kruskal-Wallis tests. Rate variables (e.g., deaths per 1,000 MVPDs) will be compared using a z-score test.

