9.4 OTHER ANALYSES

9.4.1 Safety Analyses

This study will utilize a Data and Safety Monitoring Board (DSMB) comprised of study personnel (the study PI, biostatistician, and ICU medical directors, [name]), as well as an independent medical monitor ([name], Chief of Division of Allergy, Immunology and Infectious Diseases at Robert Wood Johnson University Hospital). [name] has served on data safety and monitoring committees for multiple federally- and industry-funded clinical trials, many of which have involved the study of ventilator-associated pneumonia.

The DSMB will meet every two months to review the following safety metrics: 1) Mortality per 1000 mechanically-ventilated patient days per ICU, Ventilator- associated events (using Centers for Disease Control/National Healthcare Safety Network definitions) per 1000 mechanically-ventilated patient days per ICU, Median duration of mechanical ventilation per patient per ICU. All safety outcomes will be compared to preintervention ICU data collected over the last 5 years to ensure that postintervention values fall within 2 standard deviations of preintervention controls. The study will be halted if any safety outcome is increased by more than 2 standard deviations relative preintervention control data. If safety outcomes are decreased by more than 2 standard deviations relative to preintervention control data (i.e. in a favorable direction following the intervention), the study intervention will be continued as this is a single-arm study trial design.

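### The primary ventilator-associated event rate has two different denominators, and mortality is given only per ventilated day, with no per-patient death comparison

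*Combined protocol and SAP*

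**What the plan says.** The Section 4 primary endpoint cell lists mortality as "Mortality per 1000 mechanically-ventilated patient days" and, next to it, ventilator-associated events (VAE) as "Ventilator-associated events (using Centers for Disease Control/National Healthcare Safety Network definitions) per 1000 patient days". The synopsis words both the same way. In Section 9.4.1 the DSMB reviews "Mortality per 1000 mechanically-ventilated patient days per ICU" and "Ventilator- associated events (using Centers for Disease Control/National Healthcare Safety Network definitions) per 1000 mechanically-ventilated patient days per ICU". The halting rule then acts on these metrics: "The study will be halted if any safety outcome is increased by more than 2 standard deviations relative preintervention control data".

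The third primary endpoint is "Median duration of mechanical ventilation per patient".

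Section 9.1.1 gives the tests: "Rate variables (e.g., deaths per 1,000 MVPDs) will be compared using a z-score test" and "Subject-level continuous variables will be compared using Kruskal-Wallis tests". Section 9.2 repeats the z-test for rates and compares Feb 2022-23 with Feb 2017-22. Neither section states the VAE denominator. The chi-square sentence in 9.1.1 is generic and does not mention death. The subject-level models in 9.3 concern antibiotic use only.

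The secondary endpoint of cultures ordered has the same mismatch: patient days in the synopsis, ventilated patient days in Section 4.

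**The concern.** **(a) VAE denominator.** Read literally, the DSMB would monitor one VAE rate and the final comparison would test another, for a single primary endpoint. The two could give different messages whenever ventilator use in the units changes between periods, and the comparison spans six years.

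**(b) Mortality per ventilated day only.** The primary hypothesis (9.1.2) is that adverse safety outcomes do not significantly increase. Section 3.1.1 names underdiagnosis as the potential concern and adds that delay in effective therapy affects outcomes. The basic safety question is therefore whether more ventilated patients died. A rate per ventilated day does not answer it on its own, because its denominator is ventilation time, which the plan itself treats as a safety outcome. More deaths with longer ventilation can look like no change, and shorter ventilation with the same deaths can look like harm. The plan also leaves open whether deaths on the ventilator, in the ICU or in hospital enter the numerator.

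**Working it through.** The documents give no death rate, VAE rate, ventilation duration, ventilated share or patient count. There is no stated figure to reproduce, and every input below is an assumption.

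**(a) Denominators side by side**

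| Place | VAE | Mortality | Cultures ordered |
|---|---|---|---|
| Synopsis | patient days | ventilated patient days | patient days |
| Section 4 | patient days | ventilated patient days | ventilated patient days |
| Section 9.4.1 | ventilated patient days | ventilated patient days | not listed |

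VAE per patient day = VAE per ventilated day × ventilated share of patient days. With the ventilated-day rate constant, the pre/post ratio per patient day is therefore post share / pre share:

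- 0.50 to 0.55: 0.55/0.50 = 1.10
- 0.50 to 0.45: 0.45/0.50 = 0.90
- 0.80 to 0.85: 0.85/0.80 = 1.06

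If the share is stable it cancels and the two ratios agree.

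**(b) Mortality: the identity**

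Deaths per ventilated day = deaths per patient / mean ventilated days per patient. So mortality rate ratio = per-patient death ratio / ratio of mean ventilated days. With deaths per patient up 10%:

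| Change in mean ventilated days | Rate ratio |
|---|---|
| -10% | 1.10/0.90 = 1.22 |
| 0 | 1.10/1.00 = 1.10 |
| +10% | 1.10/1.10 = 1.00 |
| +20% | 1.10/1.20 = 0.92 |

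**Two worked cases, assuming 2500 patients before and 500 after (two-sided tests)**

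- Deaths 30% then 36%, mean ventilation 6.0 then 7.2 days. Rates: 750/15,000 and 180/3,600, both 50 per 1000 ventilated days, so p = 1.00. Proportions: pooled 0.31, z = 0.06/√(0.31 × 0.69 × (1/2500 + 1/500)) = 2.65, p = 0.008.
- Deaths 30% in both periods, mean ventilation 6 then 5 days. Rates: 750/15,000 = 50 and 150/2,500 = 60 per 1000; pooled 900/17,500 = 0.0514 per day, z = 0.010/√(0.0514 × (1/15,000 + 1/2,500)) = 2.04, p = 0.04. The proportions are identical.

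**Allowing for deaths that shorten ventilation**

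Let baseline risk be p, extra deaths e = 0.1p, and let each extra death keep a fraction f of its ventilated days. With nothing else changed, the ratio is 1.1/(1 - e + ef):

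- p = 0.2, f = 0.5: 1.111
- p = 0.4, f = 0.25: 1.134

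This makes harm slightly more visible. To bring the ratio back to 1.00, other patients' ventilation must lengthen by (1.10 - ef)/(1 - e) - 1:

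- p = 0.2, f = 0.5: 11.2%
- p = 0.4, f = 0.25: 13.5%

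**Would the duration endpoint catch it?**

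Simulated Kruskal-Wallis test at 0.05, log-normal durations with median 5 days, 3000 before and 600 after:

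| Log-SD | Uniform +10% detected | Same +10% in the mean, longest quarter only |
|---|---|---|
| 0.8 | 74% | 11% |
| 1.0 | 56% | 9% |
| 1.2 | 42% | 8% |

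These carry a few points of simulation error. In the right-hand column the longest quarter is multiplied by 1.18, 1.16 and 1.14 respectively, which leaves the median unchanged.

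**The case against.** On (a), patient days is very likely shorthand. Section 6.1 limits patient subjects to ventilated patients, and almost every other rate uses ventilated days. The ratios above need both the literal reading and a shift in ventilated share, for which the documents give no evidence. This is fair as to size. But the same cell writes the ventilated form for mortality and omits it for VAE, and nothing equates the two terms, so the text still needs correcting.

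On (b), ventilation time is already watched. Median duration is co-primary, tested at subject level, and reviewed every two months with its own halting trigger. Masking requires longer ventilation, which is what that endpoint looks for. Under the same assumptions a uniform 20% lengthening is detected in 91-100% of trials, so the first worked case would nearly always show up on duration if the lengthening were general. What remains is modest lengthening, or lengthening confined to long stays, and no text suggests the latter. The simulation covers the final test only; the sensitivity of the 2-SD trigger was not evaluated.

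The added comparison is also weak. A 10% relative rise at 20%, 30% or 40% risk is 2, 3 or 4 percentage points, and a two-proportion test at 3000 versus 600 detects it in about 20%, 31% and 45% of trials. That stands: in this pilot the proportion is for estimation, not confirmation. Even so, a duration signal does not say whether more patients died, and no other planned analysis does.

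**Conclusion.** Both parts hold. The VAE denominator is a plain contradiction in a primary endpoint, probably a slip. It is harmless to the pre/post ratio if the ventilated share is stable, and worth 6-10% in that ratio for the assumed five-point shifts.

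The mortality endpoint mixes death risk with ventilation time and has no stated numerator. A 10% rise in deaths per patient can appear as anything from 1.22 to 0.92 when mean ventilation changes by -10% to +20%. The co-primary median limits this risk but does not remove it, and it does not replace a per-patient comparison.

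The contradiction, the undefined numerator and the identity rest on the text and algebra. All magnitudes rest on assumed risks, durations, shares and patient numbers, and nothing in the documents shows that masking would occur here. The change should be made, with medium confidence in its practical importance.

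**What to change.** **(a)** Use mechanically-ventilated patient days for VAE in the synopsis and Section 4, and for cultures ordered in the synopsis, and name the VAE denominator in 9.2. Cost: wording only.

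**(b)** Keep mortality per ventilated day and state which deaths enter its numerator. Add to Sections 4 and 9.2 the proportion of ventilated patients who die, to one horizon available in both periods (for example, ICU or hospital discharge), with the pre/post difference and 95% CI. Report mean ventilation duration beside the median. If the death proportion also goes to the DSMB, the sponsor should state whether the halting rule in 9.4.1 applies to it.

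Cost: one more tabulated outcome. The mean needs no new data, because total ventilated days are already required for the rates. The team must confirm that deaths to the chosen horizon can be retrieved for 2017-22. The interval will be wide: 1.96 × √(p(1 - p)(1/3000 + 1/600)) gives about ±3.5, 4.0 and 4.3 percentage points at assumed risks of 20%, 30% and 40%.

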6.2 EXCLUSION CRITERIA

For the study intervention requiring performance of bronchoalveolar lavage rather than endotracheal aspirate for respiratory culture collection, the following are exclusion criteria for performance of bronchoalveolar lavage: INR>2, platelet count <50, gross blood in endotracheal secretions, P/F ratio<80, major lung surgery in prior 30 days. There are no exclusion criteria for study interventions at the ordering and reporting phases of the diagnostic testing pathway.

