7 STUDY INTERVENTION(S)

7.1 STUDY INTERVENTION(S) ADMINISTRATION

7.1.1 Study Intervention Description

This study's VAP diagnostic stewardship bundle will include interventions that occur at discrete phases in the diagnostic testing pathway: 1) the *preanalytic phase*, in which tests are ordered; 2) the *analytic*

phase, in which diagnostic specimens are collected and laboratory tests are performed; and 3) the postanalytic phase.

Trial Interventions

Diagnostic Testing Phase	Intervention	Implementation method	Details
Respiratory culture ordering	CDS tool requiring providers to select a valid indication for respiratory culture performance : 
 • New radiographic infiltrate on CXR or chest CT • Purulent endotracheal secretions • Worsening PEEP and/or FiO2 	Interruptive EHR alert triggered upon respiratory culture order, tagged to custom CDS order set.	The following prompts were given to providers using the CDS order set: 
 • Fever or leukocytosis without aforementioned culture indications is unlikely to indicate pneumonia. • Radiographic infiltrates consistent with atelectasis or pulmonary edema do not require respiratory cultures. • Purulent secretions are different than thickened or increased nonpurulent secretions (the latter do not require cultures). • Transient worsening of PEEP or FiO2 that rapidly improves is unlikely to indicate pneumonia
Respiratory culture collection	CDS tool requiring providers to use non-bronchoscopic BAL (performed by respiratory therapists) when no contraindications present. All BAL specimens automatically sent for quantitative respiratory culture & cell count/differential .	Interruptive EHR alert triggered upon respiratory culture order, tagged to custom CDS order set	Contraindications to BAL were as follows: 
 • major lung surgery in prior 30 days • gross blood in endotracheal secretions • INR>2 • platelet count <50k • P/F ratio <80. Consideration of bronchoscopy was recommended for sampling upper lobe infiltrates.

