Respiratory culture result reporting	Respiratory culture results automatically released in EHR only for BAL samples with a PMN% of >50% . Respiratory culture results for BAL samples with PMN% <50% released upon direct primary team request to Clinical Microbiology Lab.	Modification to Clinical Microbiology Laboratory workflows.	The following prompt was provided for suppressed respiratory culture results: 
 • "Culture results suppressed due to <50% PMNs seen in BAL, which has a sensitivity of 95% for diagnosis of bacterial pneumonia in non-neutropenic patients. Please call the Microbiology Laboratory within 7 days if identification/antimicrobial susceptibility testing are needed."

CDS=clinical decision support; EHR=electronic health record; CXR=chest X-ray; CT=computed tomography; BAL=bronchoalveolar lavage; PMN%=percentage of polymorphonuclear neutrophils observes on BAL cell count/differential.

1. Ordering (preanalytic) phase:

- Study intervention: In participating ICUs, all providers who order respiratory cultures will be automatically routed to a custom study order set within the electronic medical record. This order set will require providers to select a valid clinical indication for respiratory culture performance (worsening hypoxia, new infiltrate on chest imaging, purulent sputum production), but will not include aforementioned scenarios in which respiratory culture collection is *not* indicated (fever or leukocytosis without features localizing infection to the respiratory tract, changes in secretions that are *not* purulent, transient respiratory decompensations that rapidly improve without supportive care).

2. Collection (analytic) phase:

- Study intervention: In participating ICUs, all providers who order respiratory cultures will be automatically routed to a custom study order set within the electronic medical record. This order set will require physician or RT-guided BAL for respiratory collection rather than endotracheal aspiration for mechanically-ventilated patients, provided there are no specific exclusion criteria for individual patients (see Section 4.1 for specific patient exclusion criteria). Importantly, Respiratory Therapists are trained in the use of BAL for respiratory collection and routinely perform these procedures hundreds of times a year for precisely

this purpose. Performance of BAL is considered standard of care by national and international VAP expert guidelines.^{9,10}

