7.2 FIDELITY

7.2.1 Provider Training

Providers will be counseled on CDST use during bimonthly educational sessions over a 3-month trial rollout period and via subsequent monthly email reminders thereafter. Each ICU will designate a nursing and physician champion to facilitate implementation.

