9.2 ANALYSIS OF THE PRIMARY AND SECONDARY ENDPOINT(S)

Primary and secondary study outcomes will be compared between patient cohorts before and after DSI implementation. All primary/secondary study outcomes will compare patients admitted to study ICUs over the course of the year-long study intervention (Feb 2022-23) versus those admitted in the pre-intervention historical control period (Feb 2017-22). As above, rate variables will be compared using a z-score test. A p-value of 0.05 will be utilized for statistical significance.

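### The only measure of BAL use counts all respiratory cultures, including those from patients exempt from BAL, so by itself it cannot separate non-adherence from ineligibility

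*Combined protocol and SAP*

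**What the plan says.** Section 4 lists three endpoints under the objective "To assess study feasibility and adherence to protocolized intervention": the rate of cultures ordered, "Percentage of respiratory cultures obtained by BAL", and the percentage of BAL cultures with low alveolar neutrophils. The synopsis (Section 1.1) also lists the BAL percentage, and neither place narrows its denominator. The Section 4 justification reads "Adherence to study intervention is crucial to evaluating study efficacy and potentially recalibrating approach to intervention prior to multi-center implementation". Section 2.2 likewise names gauging and addressing adherence as a goal of the pilot.

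The collection rule is conditional. Section 6.2 states that "the following are exclusion criteria for performance of bronchoalveolar lavage: INR>2, platelet count <50, gross blood in endotracheal secretions, P/F ratio<80", and adds major lung surgery within the previous 30 days as a fifth criterion. Section 7.1.1 requires BAL "provided there are no specific exclusion criteria for individual patients". Section 6.2 also says that no exclusions apply at the ordering phase, so an exempt patient can still be cultured by another method.

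The fidelity section (7.2) covers training and delivery only, for example "Providers will be counseled on CDST use during bimonthly educational sessions over a 3-month trial rollout period and via subsequent monthly email reminders thereafter". For analysis, Section 9.2 says "Primary and secondary study outcomes will be compared between patient cohorts before and after DSI implementation". Section 9.4.2 stratifies all outcomes by ICU and implementation phase. Nothing in Section 9 analyses adherence or stratifies by BAL eligibility.

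**The concern.** Only the second of the three endpoints shows whether the collection rule was followed. The ordering rate concerns a different step, and the neutrophil percentage is conditional on BAL having been done. The rule applies to eligible patients, but the measure is taken over everyone cultured. The percentage therefore mixes three things: BAL use among eligible cultures, the share of cultures with a contraindication, and BALs done despite one.

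This matters for the use that Section 4 intends. If BAL use is low because providers bypass the rule, the response is training or a change to the alert. If it is low because many ventilated patients cannot safely have BAL, the bundle has limited reach and needs a different response before multi-center use. The crude figure does not show which applies. A BAL done in a patient with, say, a platelet count below the limit departs from Section 6.2 but raises the score, and no listed endpoint or safety metric counts such events.

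**Working it through.** The plan states no adherence figure or target, so there is nothing to reproduce. The check is an identity.

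**Inputs**
- a = share of eligible cultures obtained by BAL, which is adherence to the rule. Not in the documents.
- c = share of cultures from patients with a Section 6.2 contraindication. Not in the documents; assumed 0 to 30%.
- b = share of contraindicated cultures obtained by BAL anyway. Not in the documents; assumed 0, with 20% as a sensitivity value.
- Observed crude percentage: 70%, for illustration only.

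**Formula**

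Crude BAL% = a(1 − c) + bc, so a = (crude − bc)/(1 − c).

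One observed number cannot determine a while b and c are unknown.

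**Crude value under full adherence (a = 1, b = 0), and adherence implied by a crude 70%**

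| c | Crude value at full adherence, 1 − c | Implied a, b = 0 | Implied a, b = 20% |
|---|---|---|---|
| 0% | 100% | 0.70/1.00 = 70% | 70% |
| 5% | 95% | 0.70/0.95 = 73.7% | (0.70 − 0.01)/0.95 = 72.6% |
| 10% | 90% | 0.70/0.90 = 77.8% | (0.70 − 0.02)/0.90 = 75.6% |
| 20% | 80% | 0.70/0.80 = 87.5% | (0.70 − 0.04)/0.80 = 82.5% |
| 30% | 70% | 0.70/0.70 = 100% | (0.70 − 0.06)/0.70 = 91.4% |

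With b = 0, the gap between true adherence and the crude 70% is 0, 3.7, 7.8, 17.5 or 30 percentage points down the table. Whenever c is above zero, a crude 100% requires a = 1 and b = 1, that is, BAL in every patient whom Section 6.2 excludes.

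**Comparison between ICUs.** Suppose both units have a = 90% and b = 0, but c is 10% in one and 30% in the other (assumed). Their crude percentages are 0.90 × 0.90 = 81% and 0.90 × 0.70 = 63%. The Section 9.4.2 stratification would show an 18-point difference with identical adherence.

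**The case against.** The strongest reply is that the endpoint serves a joint objective, feasibility as well as adherence, in a population-level intervention. The BAL share of all cultures is a legitimate measure of reach, and it is the version comparable with 2017-22, when there was no BAL rule to adhere to. All of that stands, and it is why the crude percentage should stay. A reader might infer that the endpoint is wrong or should be replaced; the documents do not support that.

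A second reply is that c may be close to zero. This also stands: at c = 5% and b = 0 the crude 70% understates adherence by under 4 points. The documents do not show that the distortion is material, nor that it is negligible. Reporting c would settle it.

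A third is that stratifying by phase and ICU already gives partial information. If case mix is stable, movement in the crude percentage across phases does signal changing uptake. It still does not give the level of adherence, and it does not protect a comparison between units with different c.

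A reader might also use the Section 2.2 baseline (60% of cultures from proximal samples) to judge how much of the achievable gain has been reached. That is not supported. The figure describes ICUs at the institution and not specifically the two study units, the remaining 40% is only an upper bound for BAL, and it is not split by contraindication.

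**Conclusion.** The point holds as a limitation of a secondary measure. As an indicator of adherence to the BAL rule, the stated percentage is not identified without the contraindicated share and the BAL use among exempt patients, and the plan commits to reporting neither. The identity needs no assumption. The size depends wholly on c, b and the observed percentage, none of which the documents give: with b = 0, a crude 70% fits any adherence from 70% to 100% as c runs from 0 to 30%.

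A reader might infer that the trial's main conclusions or a progression decision are at risk. They are not. The primary safety endpoints, the antibiotic outcomes and the halting rule in Section 9.4.1 do not use this percentage, and no adherence threshold is set. What is lost is the information that Sections 2.2 and 4 say the pilot should supply for recalibrating the bundle.

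**What to change.** Keep the crude percentage for the pre/post comparison. Add to Section 4, for the intervention year, overall and by ICU:

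1. BAL cultures divided by respiratory cultures in mechanically ventilated patients with no Section 6.2 contraindication at order time.
2. The share of cultures with a contraindication.
3. The number of BALs done despite one.

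Take INR, platelets, P/F ratio and recent major lung surgery from the record, so that a provider's selection of a contraindication cannot by itself remove a culture from the denominator. For the three measured values, use the last result in a stated look-back window (for example 24-48 hours); surgery keeps its own 30-day window. Treat a missing value as no contraindication, with a sensitivity analysis that excludes those cultures. Include gross blood only if the order set records it, which the documents do not say. Otherwise state that cultures exempt only for gross blood remain in the denominator and understate adherence by an unknown amount.

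The cost is modest chart extraction for one year of cultures and some misclassification of eligibility. The new rate has no counterpart in the historical period, so it supplements the pre/post comparison and does not replace it.
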